4.4. Assent Process: N/A

4.5. Benefits:

There may be no direct benefits to the subjects for participating in this study.

4.6. Risks:

The potential risks to participate in this study are minimal. The risks of auricular acupuncture associated with participating in this research study include:

LIKELY: Likely and not serious:

- Pain
- Bleeding

LESS LIKELY: Less Likely and not serious:

- Infection

4.7. Costs: N/A

4.8. Safeguards for Protecting Information:

The research consents will be stored in a locked cabinet in a locked room. Medical records will be annotated with ICD-10 code Z00.6 to reflect the subject's participation in a research study. All research data including patient demographics will be kept in an electronic database, which will be encrypted, double password protected and the access will be restricted. The research data will be coded and any links to identifiable data will be destroyed as soon as the Final Report Approval has been obtained from the IRB with the exception of those that consent to place their study-related PHI/PII into the "Nellis Acupuncture Research Data Repository (FWH20140048H)" for future research. The anonymized research data will not be utilized for further research activity beyond the protocol stipulations without additional IRB approval.

4.9. Safeguards for Protecting Subjects:

The principal investigator will be responsible for the protocol safety monitoring. The PI will make study documents (e.g., consent forms, data pulls) and pertinent hospital or clinical records readily available for inspection by the local IRB and oversight staff for confirmation of the study data.

4.9.1. Minimizing Risks:

These risks will be minimized by cleaning the acupuncture site with an alcohol swab prior to placement. If at any time the patient reports a side effect, they will be referred to one of the Investigators for care.

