Various levels of acupuncture training have been taught to several hundred military physicians. A barrier to more widespread implementation has been lack of scientifically rigorous clinical trials to prove its worth in spite of the wide variety of anecdotal reports purporting its value in treating migraine. This trial will establish the efficacy acupuncture for acute migraine so that military beneficiaries can use less mind-altering medications. Additionally, many patients who have experienced traumatic brain injury develop chronic migraine that is refractory to medication, and acupuncture could be an important adjunct to this malady. Finally, management of medication side effects (i.e. chest pain in patients who take triptans) adds to costs that could be averted if acupuncture is effective. Proof that acupuncture is an effective treatment for acute migraine in military beneficiaries could result in fewer lost duty days, decreased medication use, and improved quality of life.

3.5. Background and Review of Literature:

Migraine is a recurring disorder characterized by attacks of severe headache generally associated with nausea, vomiting, and other neurologic symptoms. Duration is usually more than 4 hours and may last up to 72 hours with fluctuating intensity.¹ Migraine is commonly characterized as either episodic or chronic, depending on the frequency of attacks. Episodic migraine is more common, affecting up to 12% of the general population.² The direct medical costs of migraine headaches are approximately \$1 billion per year in the U.S.,³ with a national annual indirect burden of migraine estimated at \$12 billion (mostly attributed to absenteeism).³

Management of migraine focuses both on the treatment of acute attacks and the prevention of such attacks.^{4,5} The goals of migraine preventive therapy are to reduce attack frequency, severity, and duration; improve functional status/reduce disability; and improve response to acute treatments. The goal of acute treatment is typically to quickly eliminate or reduce the severity of migraine headache pain and associated symptoms. People who experience frequent migraine episodes often overuse

symptomatic medications. There are many “rescue medications” to choose from for the acute treatment of migraine, but side effects from pharmacologic approaches to migraine treatment can be considerable and often limit treatment options.

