- Review past medical history in Armed Forces Health Longitudinal Technology Application (AHLTA) to verify the inclusion/exclusion criteria including previous encounter, vital signs review, medication list, co-morbidities, demographics, problems list, and note any prior acupuncture received. (research only)
- Record: Date of birth, age, gender, race, ethnicity, last 4 of social security number, name of standard of care rescue medications (over-the-counter and prescription), current email address (to be used for scheduling only), height (in

inches), weight (in pounds), history of traumatic brain injury, concussion, or any mild to severe head trauma, medication use, history of acupuncture. (research only)

- We will ask what the subjects expectations are regarding acupuncture's effectiveness for migraine. (research only)
- We will instruct subjects not to take their over-the-counter and prescription headache medications until after their visit with the research staff. (Standard care)
- We will instruct subjects to bring their over-the-counter and prescription headache medications with them to each visit if their symptoms do not resolve from the acupuncture treatment. (research only)
- Patient will be instructed to contact the Research Coordinator, as soon as possible, after onset of migraine symptoms (including prodromal symptoms) to schedule an emergent visit with the research staff. (research only)
- Patient will be given a contact card with the names and phone numbers of the research staff to contact when they have a migraine episode.

Migraine Episode:

- Self-reported headache pain severity (0=no headache, 1=mild, 2=moderate, 3=severe) (Standard care)
- Record type and amount of rescue medications (over-the-counter and prescription) use in the past 7 days. (research only)
- Acupuncture treatments will be subject dependent, and points could include the N point (on scalp); various auricular points to include Shen Men, Point Zero, thalamus and Omega-2; body points to include Liver 2, Liver 3, Gall Bladder 20, bladder 10; and surface release over tense areas in the neck or shoulders. (Standard care)
- Researchers will document the points used. (Standard care)
*If after 20-30 minutes these patients have not had resolution of their headache, they may take their standard of care rescue medication. (research only)
- The subject will sit for 20-30 minutes post-acupuncture(research only), and then the needles will be removed and the subject will be asked:

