 - Self-reported headache pain severity (0=no headache, 1=mild, 2=moderate, 3=severe) (research only)
- Subject is allowed to leave and will be informed of the following telephone follow ups:
- 2 Hours post acupuncture:
 - Self-reported headache pain severity (0=no headache, 1=mild, 2=moderate, 3=severe) (research only)
- 4 Hours post acupuncture:
 - Self-reported headache pain severity (0=no headache, 1=mild, 2=moderate, 3=severe) (research only)
- 24 Hours post acupuncture:
 - Self-reported headache pain severity (0=no headache, 1=mild, 2=moderate, 3=severe)
 - Would you use acupuncture for future pain management? (Yes or no)
 - Would you prefer acupuncture or your rescue meds (both over-the-counter and prescription) for future episodes?
 - Record type and amount of rescue medications (over-the-counter and prescription) used since acupuncture. (research only)

Patients with missed phone calls will not be withdrawn from the study. If there is a missed call, we will mark as 'missed', including the reason and continue with the next phone call.

The Research Coordinator will record the name of the AI performing the acupuncture and also the placement of the acupuncture needles for each migraine episode.

Placement of Acupuncture:

[figure not shown]
Acupuncture treatments will be subject dependent, and points could include the N point (on scalp) (Figure 1); various auricular points to include Shen Men(Figure 2), Point Zero(Figure 3), thalamus(Figure 4) and Omega-2(Figure 5); body points to include Liver 2(Figure 6), Liver 3(Figure 6), Gall Bladder 20(Figure 7), bladder 10(Figure 7); and surface release over tense areas in the neck or shoulders. We will utilize the Seirin J-Type Acupuncture needles (Figure 98). Intermittent placement checks by the medical acupuncturist will be performed.

This study will follow all FDA requirements for the safe use of these devices.

Only the investigators listed on this study will perform the insertion of the acupuncture needles. All investigators are trained in this acupuncture technique and credentialed by the Credentials committees.

The Food and Drug Administration (FDA) regulates acupuncture needles as a class II medical device, because they are intended for use in the cure, mitigation, treatment, or prevention of disease in man or are intended to affect the structure or function of the body of man. The FDA regulates the acupuncture needles (see 21 CFR 880.5580), but not the practice of acupuncture itself.

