4.9.2. Vulnerable Populations: N/A

4.9.3. Clinical Care:

All subjects will receive standard of care regardless of inclusion into this study. If at any time a subject experiences any injury or adverse effects, appropriate clinical care will be given or subject will be referred to appropriate provider.

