4.9.4. Injury Compensation: N/A

4.9.5. Data Safety Monitoring:

The principal investigator will be responsible for the protocol safety monitoring. The PI will make study documents (e.g., consent forms, data pulls) and pertinent hospital or clinical records readily available for inspection by the local IRB and oversight staff for confirmation of the study data.

5.0. Alternatives:

Acupuncture for migraine is done in the Family Medicine Residency as part of standard of care. Subjects may choose to get this type of acupuncture without participating in this study.

6.0. Data Analysis:

6.1. Outcome Measures:

Primary outcome: Reduction of migraine headache pain from mild, moderate or severe to pain free, 20-30 minutes, 2 hours, 4 hours and 24 hours post treatment. Secondary outcomes: patient global assessment of preference for trying acupuncture vs rescue medications; overall satisfaction and perceived effectiveness of the treatment; reduction of symptoms other than migraine headache pain; and use of rescue medication within 12 hours of the initial treatment (irrespective of which study treatment received). These standardized outcome measures are commonly used in comparative effective trials of migraine rescue medications. Researchers will document the points used, and data will be aggregated to determine overall effectiveness. Sub-group analysis by points will be performed to determine if there is more usefulness in 1 point or combination of points.

6.2. Sample size estimation/power analysis:

We will treat 30 subjects. We will administer up to 6 acupuncture treatments for up to 6 different migraine episodes per subject over the course of 3 months. We will not formally test a hypothesis. Rather, we will determine the proportion of migraines that resolve (as assessed by headache severity) 20-30 minutes, 2 hours, 4 hours, and 24 hours after the start of an acupuncture treatment. These data will be used to inform power calculations for future studies.

6.3. Statistical Analysis:

We will use descriptive statistics to characterize the clinical response of subjects after acupuncture treatments.

6.4 Number of Subjects:

Number of subjects planned for MOFMC	Enrolled in Study	60	to result in	30	completing the study.
--------------------------------------	-------------------	----	--------------	----	-----------------------

TOTAL NUMBER OF SUBJECTS (nation-wide/study-wide): 60

7. **Duration of Study:** Approximate duration of the study: 2 years

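### No scheduled contact asks about side effects and no section says they are recorded, so no adverse-event rate is planned and any crude rate would be a lower bound

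*Combined protocol and SAP*

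**What the plan says.** All references are to the combined protocol and SAP.

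- **Handling of side effects.** Section 4.9.1 (Minimizing Risks): "If at any time the patient reports a side effect, they will be referred to one of the Investigators for care". Section 4.9.3 (Clinical Care): "If at any time a subject experiences any injury or adverse effects, appropriate clinical care will be given". Section 4.9.5 (Data Safety Monitoring): "The principal investigator will be responsible for the protocol safety monitoring". None of the three names a form, a definition, a time window or a summary.
- **Questions asked.** In section 3.6, the contacts at 20-30 minutes, 2 hours and 4 hours collect headache severity only. The 24-hour call adds future use of acupuncture, preference against rescue medication, and rescue medication taken.
- **Outcomes and analysis.** The secondary outcomes in 6.1 cover preference, satisfaction, perceived effectiveness, relief of other symptoms and rescue medication. Section 6.3 plans descriptive statistics of clinical response. Neither has a safety item.
- **Risks and sites.** Section 4.6 introduces its list with "The risks of auricular acupuncture associated with participating in this research study include" and gives pain, bleeding and infection. Section 3.6 allows scalp and ear points and also "body points to include Liver 2, Liver 3, Gall Bladder 20, bladder 10; and surface release over tense areas in the neck or shoulders".
- **Rationale.** Section 3.4 argues that "management of medication side effects (i.e. chest pain in patients who take triptans) adds to costs that could be averted" if acupuncture works.

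**The concern.** The study is meant to supply planning figures for a randomised trial of acupuncture against rescue medication, and the side effects of medication are part of the stated case for acupuncture. A tolerability figure for the acupuncture arm would be a natural by-product, because staff are with the subject while the needles are in place and telephone three times in the next 24 hours. As written, those contacts collect nothing on harms.

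This cannot be repaired at analysis, since answers to a question that was never asked cannot be recovered. Minor or delayed problems could go unseen over as many as six treatments per subject, including at body, neck and shoulder sites. The plan will look for points that are more useful than others, with no harms data by site to set beside that.

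**Working it through.** **1. Is there any place for a side-effect item?** The plan gives no adverse-event figure to reproduce, but the procedure table in 3.6.5 can be checked against the schedule in 3.6, at six episodes per subject:

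| Item | Contacts per episode | 6 x contacts | Table total |
|---|---|---|---|
| Pain severity | 5 (before treatment, 20-30 min, 2, 4, 24 h) | 30 | 30 |
| Future use | 1 | 6 | 6 |
| Preference | 1 | 6 | 6 |
| Rescue medication | 2 (before treatment, 24 h) | 12 | 12 |

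The table accounts for every scheduled question, and none concerns side effects. The pain item is about headache, so it does not pick up pain from needling. The secondary outcome on other symptoms concerns their reduction after treatment, not new harms.

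**2. What would volunteered reports give?** The observed rate is the true rate multiplied by the share of events reported, and that share is unknown. Illustration with assumed values: a true rate of 10% per treatment and a share of 20% to 100% give an observed rate of 2% to 10%. In 180 treatments that is 180 x 0.02 = 3.6 to 180 x 0.10 = 18 reports. The same true rate fits both counts, so the true rate cannot be recovered.

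**3. How many treatments could there be?** Section 6.2 gives 30 subjects treated, up to 6 treatments each, over 3 months.

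- Ceiling: 30 x 6 = 180.
- If the cadet rates in 3.4 applied (0.70 migraines a month in men, 1.4 in women) and every attack were treated: 0.70 x 3 = 2.1 and 1.4 x 3 = 4.2 per subject, so 30 x 2.1 = 63 to 30 x 4.2 = 126.

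**4. What could solicited data show?** With zero events in n, the exact one-sided 95% upper limit is 1 - 0.05^(1/n).

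| Unit | n | Upper limit |
|---|---|---|
| Subjects | 30 | 9.5% |
| Treatments, independent | 63 | 4.6% |
| Treatments, independent | 126 | 2.3% |
| Treatments, independent | 180 | 1.7% |

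**5. Allowance for repeat episodes.** With six treatments per subject the design effect is 1 + 5 x ICC, and the effective n is 180 divided by it. The ICC values are assumptions.

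| ICC | Design effect | Effective n | Upper limit |
|---|---|---|---|
| 0.1 | 1.5 | 120 | 2.5% |
| 0.3 | 2.5 | 72 | 4.1% |
| 0.5 | 3.5 | 51.4 | 5.7% |
| 1 | 6 | 30 | 9.5% |

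**The case against.** **Events are not wholly dependent on a complaint.** Section 4.9.3 applies when a subject experiences an adverse effect, whether or not it is reported. The principal investigator is responsible for safety monitoring, and subjects stay on site until the needles come out, so staff could see immediate bleeding or pain. This stands as far as care goes, and it would be wrong to infer that the plan ignores harms. It does not supply a record: none of these provisions says that an event is written down or counted.

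**A rate is still possible.** A reader might infer that the study can give no adverse-event rate at all because there is no valid denominator. The documents do not support that. Section 3.6 has the acupuncturist and needle placement recorded for each episode, so treatments can be counted. If volunteered events were logged, they would give a crude lower bound. The weakness is the incomplete numerator.

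**The study is exploratory and its aim is headache response.** Acupuncture is described as standard care at the site, no hypothesis is tested, and the main estimate is the proportion of episodes that become headache-free. That estimate is unaffected, so this is an improvement and not a threat to the primary objective. An exploratory study can still describe tolerability, at contacts it already makes.

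**The risk wording is mainly drafting.** Pain, bleeding and infection could occur at any needled site, and 4.9.1 speaks of the acupuncture site in general. That is fair. The mismatch between 4.6 and 3.6 is a separate point, and the narrow list does not cause the missing rate.

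**Unseen material.** The consent document and the device form listed as attachments were not available. They may hold wider risk text or event-reporting rules.

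**Conclusion.** The concern holds in limited form. In the protocol as available, side effects are not asked about at any scheduled contact, and no section provides for recording or summarising them. No adverse-event rate is therefore planned. A crude rate from volunteered events would understate the true rate by an unknown amount, and an absence of reports would not show an absence of events.

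Solicited data would give modest but usable precision. If no event were seen, the upper limit would be 9.5% per subject. Per treatment it would be about 4.6% to 1.7% over 63 to 180 treatments under independence, rising to 5.7% at 180 treatments with an assumed ICC of 0.5. The range of 63 to 126 should not be read as the plan's expected count. It borrows rates from cadets in training, while subjects here must already have been prescribed rescue medication, and it assumes that every attack is treated. The ceiling of 180 is the only treatment total that follows from the plan itself.

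A reader might also infer from the rationale in 3.4 that the study could have tested whether acupuncture has fewer side effects than medication. It could not, because there is one arm. It can offer only a planning estimate for the randomised trial.

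**What to change.** 1. Add one scripted item to the 20-30 minute assessment and the 24-hour call: *Any problem from the needling? What, body site, severity, resolved or not.* Ask it again at the next episode visit, to pick up later events such as infection. A subject's last treatment has no later visit, so late events after it would remain unsolicited; the report should say so.
2. Add a row to the procedure table in 3.6.5, and state that volunteered and observed events are recorded in the same place, marked as unsolicited.
3. Add to 6.1 a descriptive secondary outcome: adverse events per treatment and per subject, by needling site. Give exact intervals per subject, and per-treatment intervals that allow for repeat episodes within a subject. With no or very few events, rely on the per-subject limit.
4. Separately, reconcile the risk description in 4.6 with the scalp, body, neck and shoulder sites in 3.6.

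The cost is one question at contacts already made, one table and a minor amendment, with no new visits and no change in sample size. The downside is that more minor events will be recorded.

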4.9.2. Vulnerable Populations: N/A

4.9.3. Clinical Care:

All subjects will receive standard of care regardless of inclusion into this study. If at any time a subject experiences any injury or adverse effects, appropriate clinical care will be given or subject will be referred to appropriate provider.

4.9.4. Injury Compensation: N/A

4.9.5. Data Safety Monitoring:

The principal investigator will be responsible for the protocol safety monitoring. The PI will make study documents (e.g., consent forms, data pulls) and pertinent hospital or clinical records readily available for inspection by the local IRB and oversight staff for confirmation of the study data.

5.0. Alternatives:

Acupuncture for migraine is done in the Family Medicine Residency as part of standard of care. Subjects may choose to get this type of acupuncture without participating in this study.

6.0. Data Analysis:

6.1. Outcome Measures:

Primary outcome: Reduction of migraine headache pain from mild, moderate or severe to pain free, 20-30 minutes, 2 hours, 4 hours and 24 hours post treatment. Secondary outcomes: patient global assessment of preference for trying acupuncture vs rescue medications; overall satisfaction and perceived effectiveness of the treatment; reduction of symptoms other than migraine headache pain; and use of rescue medication within 12 hours of the initial treatment (irrespective of which study treatment received). These standardized outcome measures are commonly used in comparative effective trials of migraine rescue medications. Researchers will document the points used, and data will be aggregated to determine overall effectiveness. Sub-group analysis by points will be performed to determine if there is more usefulness in 1 point or combination of points.

6.2. Sample size estimation/power analysis:

We will treat 30 subjects. We will administer up to 6 acupuncture treatments for up to 6 different migraine episodes per subject over the course of 3 months. We will not formally test a hypothesis. Rather, we will determine the proportion of migraines that resolve (as assessed by headache severity) 20-30 minutes, 2 hours, 4 hours, and 24 hours after the start of an acupuncture treatment. These data will be used to inform power calculations for future studies.

6.3. Statistical Analysis:

We will use descriptive statistics to characterize the clinical response of subjects after acupuncture treatments.

6.4 Number of Subjects:

Number of subjects planned for MOFMC	Enrolled in Study	60	to result in	30	completing the study.
--------------------------------------	-------------------	----	--------------	----	-----------------------

TOTAL NUMBER OF SUBJECTS (nation-wide/study-wide): 60

7. **Duration of Study:** Approximate duration of the study: 2 years

8. **Local and External Support Services:** None

9. **Intramural (GME) and Extramural Funding Support:** None

10. **Conflict of Interest:** No financial, personal, or off duty employment conflicts of interest exist.

11. **Use of an Investigational New Drug, use of a Drug for a non-FDA approved purpose, use of an investigative device or use of a placebo:**

This research uses an Investigational New Drug	 YES	 NO
This research uses a FDA approved drug for a non-FDA approved purpose	 YES	 NO
This research uses an Investigational Device	 YES	 NO
This research uses a placebo.	 YES	 NO

12. **Medical Research Area for the Study:** (Pick as many as appropriate)

 Analytical Chemistry	 Anatomy	 Anesthesiology	 Biochemistry
 Cardiovascular Surgery	 Cardiology	 Cell Biology	 Dentistry
 Dermatology	 Dietetics	 Electrophysiology	 Endocrinology
 Emergency medicine	 Gastroenterology	 General Surgery	 Hematology
 Histology	 Immunology/Allergy	 Infectious Disease	 Microbiology
 Molecular Biology	 Neonatology	 Neurology	 Neurosurgery
 Nursing	 OB/GYN	 Occupational Medicine	 Occupational Therapy
 Oncology	 Ophthalmology	 Oral/Maxillofacial Surgery	 Orthopedics
 Pathology	 Pediatrics	 Pharmacology	 Physical Therapy
 Mental Health	 Radiology/Imaging	 Urology	 Wellness
 Other (state): Family Medicine			

13. **Attachments:**

1. Contact Card
2. Certificate of Compliance
3. Informed Consent Document
4. HIPAA Authorization Document
5. Use of an Investigational Device in Research
6. Advertisement
7. Form A2 Study personnel
8. Application checklist

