This will be an exploratory observational trial of rescue acupuncture for the treatment of acute migraine in military beneficiaries to gain information to inform the power analysis of a larger, more definitive trial. We do not seek to definitively answer the question of whether this acupuncture protocol is effective; rather, we seek to estimate the proportion of migraine episodes that result in headache-free status 20-30 minutes, 2 hours, 4 hours, and 24 hours after an acupuncture treatment. Acupuncture treatments will be subject dependent, and points could include the N point (on scalp); various auricular points to include Shen Men, Point Zero, thalamus and Omega-2; body points to include Liver 2, Liver 3, Gall Bladder 20, bladder 10; and surface release over tense areas in the neck or shoulders. Researchers will document the points used, and data will be aggregated to determine overall effectiveness. Sub-group analysis by points will be performed to determine if there is more usefulness in 1 point or combination of points. These estimates will inform statistical power calculations for a future randomized controlled trial (RCT) that directly compares the effectiveness of Rescue Acupuncture with medical management of acute migraine with rescue medication. We will also assess the feasibility of this study protocol as well as patient receptivity and satisfaction.

5. Subjects:

Male and female DoD beneficiaries ages 18 years or older will be recruited at the Mike O’Callaghan Federal Medical Center (MOFMC). No special populations (e.g., pregnant women, children, military basic trainees, prisoners, detainees) will be recruited.

6. Inclusion/exclusion criteria:

Inclusion:

- Male and female DoD beneficiaries, age 18 years or older, who have been previously prescribed rescue medication to treat their acute migraine episodes.

Exclusion:

- Pregnant
- Absence of ear
- Active cellulitis of ear
- Ear anatomy precluding identification of acupuncture landmarks
- Use of Hearing Aids that preclude the insertion of needles

- Use of anticoagulants
- Unable to drive during rapid onset of migraine or inability to find someone to drive you

7. Number of Subjects: TOTAL NUMBER OF SUBJECTS (nation-wide/study-wide): 60

8. Use of an Investigational New Drug: N/A

9. Use of an Investigational Device: Seirin J-Type Acupuncture needles and Sedatelec ASP Original Gold Acupuncture needles, 510(k) exempt as Class II device under 21 CFR 880.5580

10. Use of a Placebo: N/A

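### The pain-free proportion is pooled over mild, moderate and severe starts with no breakdown by the recorded starting severity, so it may not carry over to an RCT with a different mix

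*Combined protocol and SAP*

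**What the plan says.** Section 6.1 gives the primary outcome as "Reduction of migraine headache pain from mild, moderate or severe to pain free", judged at each of four follow-up times. Section 6.2 turns this into a single figure per time point: "we will determine the proportion of migraines that resolve (as assessed by headache severity) 20-30 minutes, 2 hours, 4 hours, and 24 hours after" treatment begins. Section 6.3 is one sentence: "We will use descriptive statistics to characterize the clinical response of subjects after acupuncture treatments".

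The figure has a stated use. The Brief Summary says "These estimates will inform statistical power calculations for a future randomized controlled trial (RCT" comparing acupuncture with rescue medication, and section 6.2 repeats the planning purpose.

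Three other features matter:

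- **Entry.** The criteria in section 3.6.7 ask for an adult beneficiary with a prior rescue prescription. Neither they nor the Migraine Episode steps in section 3.6 set a minimum pain level for treatment.
- **Timing.** Under Screening Visit in section 3.6: "Patient will be instructed to contact the Research Coordinator, as soon as possible, after onset of migraine symptoms (including prodromal symptoms" included.
- **Baseline.** Under Migraine Episode in section 3.6, the first item is "Self-reported headache pain severity (0=no headache, 1=mild, 2=moderate, 3=severe) (Standard care", so a starting rating exists for every episode.

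The only sub-group analysis named (Brief Summary, 3.6.1 and 6.1) is by acupuncture point. Section 3.2 states the objective as change in pain severity, which does use the starting rating, but 6.1 to 6.3 do not turn that into an analysis by starting severity.

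**The concern.** An attack that goes from 1 to 0 and one that goes from 3 to 0 count equally. That is normal for a pain-free endpoint and is not itself an error. But the pooled proportion is a weighted average of severity-specific rates, and the weights are whatever mix of attacks happens to arrive. The documents do not say what starting severity or time to treatment the RCT will have. If its mix differs and the rates differ by severity, the pooled figure is the wrong input to the power calculation, which is this study's main declared purpose.

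The point sub-groups face a related risk. Points are chosen subject by subject. If the choice follows presenting severity, a point used mostly for milder attacks will look more useful than it is.

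**Working it through.** **The plan's own figures.** Section 6.4 gives 60 enrolled to yield 30 completing. The plan states no alpha, power, response rate or precision target, so no stated figure depends on the pooling and none can be shown wrong. The most episodes possible is 30 × 6 = 180.

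**Does the mix matter?** The documents give no severity distribution or response rates, so everything below is assumed.

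Pooled rate = Σ (share of severity × pain-free rate in that severity)

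| Assumed rates, mild/moderate/severe | Mix 60/30/10 | Mix 0/60/40 |
|---|---|---|
| 35/35/35% | 35% | 35% |
| 45/35/25% | 0.6×45 + 0.3×35 + 0.1×25 = 40% | 0.6×35 + 0.4×25 = 31% |
| 60/35/20% | 0.6×60 + 0.3×35 + 0.1×20 = 48.5% | 0.6×35 + 0.4×20 = 29% |

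The same treatment gives rates 0, 9 or 19.5 points apart, depending only on the gradient and the mix. The middle row also shows the sub-group problem: two points with identical effects, one used in the first mix and one in the second, would report 40% and 31%.

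**Against sampling error.** The 95% half-width at a 40% rate is 1.96 × √(0.24/n):

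- n = 180 independent episodes: 7 points.
- Assumed within-subject correlation 0.3: design effect 1 + 5×0.3 = 2.5, effective n = 180/2.5 = 72, 11 points.
- One episode per subject, n = 30: 18 points.

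A 9-point shift is of similar order to these half-widths.

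**Consequence for an RCT.** Use the middle row, two-sided 5%, 80% power, 1:1:

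n per arm = [1.96√(2p̄(1−p̄)) + 0.8416√(p₁(1−p₁) + p₂(1−p₂))]² / (p₁−p₂)²

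Suppose the RCT is planned on 40% against an assumed comparator of 20%. Then n = 1.8025²/0.04 = 81.2, or 82 per arm. Suppose it then enrols only moderate and severe attacks, so the acupuncture rate is 31%. The result depends on what the comparator does:

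| Comparator in the RCT | Comparison | Needed per arm | Power with 82 |
|---|---|---|---|
| Stays at 20% | 31 v 20% | 246 | 36% |
| Keeps its ratio to acupuncture (0.5) | 31 v 15.5% | 116 | 65% |
| Keeps its difference (20 points) | 31 v 11% | 64 | 89% |

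The same shift in the acupuncture rate can leave the RCT badly undersized, moderately undersized or slightly oversized.

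**Precision of the proposed strata.** If 180 episodes split evenly, each of three strata has 60, with a half-width of 12 points at 40% before any clustering. As a lower assumption, the cadet migraine rates in section 3.4 (0.70 to 1.4 per month) give 30 × 3 × 0.70 = 63 to 30 × 3 × 1.4 = 126 episodes. That is 21 to 42 per stratum, with half-widths of about 21 to 15 points.

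**The case against.** The strongest reply is that this is an exploratory study that disclaims hypothesis testing, and that descriptive statistics leave room for a table by severity. If the RCT keeps the same rule (early contact, any severity), the pooled proportion is the right planning rate for its acupuncture arm. Stratum rates from a few dozen clustered episodes could be less reliable than the pooled one. All of this stands. It limits the point to a conditional one and rules out asking that the pooled rate be set aside. It does not remove the gap: room for a table is not a plan for one, and whether a gradient exists cannot be seen from the pooled figure.

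A reader might infer two stronger things.

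- **That early contact makes the sample mild-heavy, so the pooled rate is too high.** The documents do not establish this. After calling, the subject must arrange a visit and travel to the clinic, and is told not to take headache medication until after it. The rating is taken at that visit, by which time the pain may have risen. A milder mix is possible, not certain.
- **That the RCT would be several times too small.** That follows only if the comparator rate is held fixed while the acupuncture rate moves with severity. If severity affects being pain free under acupuncture, it may well do so under rescue medication too, and the last table shows how far the answer then changes.

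**Conclusion.** The point holds as a gap in the planned analysis and reporting, not in data collection. Sections 6.1 to 6.3 pool over a starting severity that is recorded for every episode, set no minimum severity, and plan no breakdown by it, while the result is intended for RCT planning. Harm to the planning value needs two conditions: a pain-free rate that differs by starting severity, and an RCT with a different mix. Confounding of the point sub-groups needs the first condition and a choice of points related to severity.

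The documents fix neither direction nor size. On assumed gradients the pooled rate moves by 0 to 19.5 points, and the effect on RCT sample size depends on how the comparator behaves. The overall proportion remains valid as a description of the attacks treated. The change is worth making because it is cheap and bears directly on what this study can pass on. Attacks rated 0 on arrival raise a separate denominator question, not covered here.

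**What to change.** In sections 6.1 and 6.3, add:

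1. The distribution of pre-treatment severity over treated episodes.
2. The pain-free proportion at each time point within pre-treatment severity, collapsed to mild versus moderate/severe if cells are small. Give numerators, denominators and intervals that allow for repeated episodes per subject, beside the overall figure.
3. The starting-severity mix for each point sub-group.
4. A sentence saying that RCT planning will consider the stratum rates, reweighted to the RCT's entry severity if that differs, together with the pooled rate.

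The cost is some added wording and one extra table; no new data are needed. The drawback is imprecision: at most 180 clustered episodes are divided among the strata, so their rates should be presented as rough inputs with their intervals.
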